Participating GP surgeries will only be informed of their patient's participation in the study following receipt of informed consent. All data storage and handling will follow the principles of good clinical practice. All human tissue samples will be labelled anonymously and stored in accordance with the Human Tissue Act (2004).

4. Objectives and Outcome Measures

Primary Objectives:

The primary aim of the research is to assess the feasibility of conducting a randomised control trial to evaluate the effectiveness of a focused 15-minute one-to-one consultation in a primary care setting with a health-care professional to improve blood glucose control in pre-diabetes.

The study aims to quantify the following:

- the number of patients with an HbA1c between 42 and 47 mmolmol⁻¹ during the recruitment phase
- the percentage of patients eligible to participate who gave consent to be part of the study
- the percentage of patients who completed baseline testing; 3 month; and 6 month testing

Secondary Objectives

Secondary research questions aim to determine the impact of the consultation on the following measures at 3 and 6 months:

HbA1c

Cholesterol

BMI

Waist and hip girth

Blood pressure

Body composition

Physical activity level

Dietary habits

5. Study Design

This feasibility study will use a randomised control design to assess the effectiveness of a 15 minute one to one consultation compared to no treatment.

6. Study Setting:

All research activity included in the baseline, 3 month and 6 month visits will be completed within the [name], Aberystwyth University. The 15 minute pre-diabetes consultations will take place within Church Surgery, Aberystwyth.

7. Participant Eligibility

Participants will be eligible for participation if they are registered with Church Surgery and have an HbA1c (recorded within the last year) of between 42 and 47 mmol⁻¹.

8. Inclusion and Exclusion Criteria

Inclusion Criteria	Exclusion Criteria
Age > 18, < 80	Under judicial control
Able to provide consent	Unable to understand and follow instructions due to cognition or language problems or provide consent
Registered with a mid-Wales GP surgery	
HbA1c between 42 mmol·mol ⁻¹ and 47 mmol·mol ⁻¹	

9. Participant Identification and Recruitment

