Further information regarding the study can be sought via telephone, email or visiting the university research facility in person. Any questions the participant may have can be asked at any point prior to giving consent using any of these methods. Patients are free to withhold consent without giving reason. In accordance with the Welsh Language Act 1993, all correspondence will be translated into Welsh. For patients confirming their involvement, verbal and written informed consent will be sought in person at the start of their first visit to the Well-being Assessment Research Unit (WARU) before being inducted into the study (> 24 hours between receipt of the

study invite letter & participant information sheet and signing informed consent). Those who decline involvement will receive usual care from their GP.

13. Study Procedures

Participants will be required to visit the WARU ([name]) on 3 separate occasions, for baseline, 3 month and 6 month testing. During the baseline visit, the procedures and protocol of the study will be explained and informed consent will be received. Participant's height (Holtain Ltd, Crymych, UK) and body mass (wearing loose fitting clothing; Seca 899, Hamburg, Germany) will be collected to calculate body mass index (BMI) and waist and hip girth recorded (Seca 201, Seca GmbH & Co, Hamburg, Germany). Next, participants will be asked to sit quietly for 10 minutes in the laboratory before blood pressure is recorded from the upper non-dominant arm (Omron M3, Omron Healthcare Ltd, Milton Keynes, UK). Participants will remain seated prior to a 6 mL blood sample being obtained from the antecubital vein and collected into a heparinised vacutainer (BD Vacutainer Systems, Plymouth, UK), with minimal stasis, using standard venepuncture methods performed by a trained member of the research team. Should patients HbA1c be outside the required values during the baseline visit, they will be informed and will take no further part in the research. WARU will inform the participant's GP if their HbA1c is indicative of diabetes. Body composition will be analysed using bioelectrical impedance (Bodystat 1500, Bodystat Ltd, Douglas, British Isles).

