Administration of the International Physical Activity Questionnaire Short Form	3	10 minutes	[name] or other member of the research team. This will take place in the [name] at Aberystwyth University
Administration of the Food Frequency Questionnaire	2	15 minutes	[name] or other member of the research team. This will take place in the [name] at Aberystwyth University
36-Item Short Form Health Survey Instrument	3	10 minutes	[name] or other member of the research team. This will take place in the [name] at Aberystwyth University
Components of the Personal Diabetes Questionnaire	1	10 minutes	[name] or other member of the research team. This will take place in the [name] at Aberystwyth University
15 minutes pre-diabetes consultation (if randomised to receive)	1	15 minutes	Performed by a practice nurse at a mid-Wales General Practise
End of Study Feedback questionnaire	1	10 minutes	[name] or other member of the research team. This will take place in the [name] at Aberystwyth University

18. Withdrawal Criteria

Participants are free to withdraw from the study at any time without giving prior warning or reason for withdrawal. Participants will not be replaced if withdrawn. Recruitment will continue for the first 6 months of the study. New participants will receive unique individual participant numbers.

19. Storage and Analysis of Clinical Samples

Blood Treatment:

A 1 mL aliquot of whole blood will be transferred from the heparinised vacutainer into a 1.5 mL Eppendorf. The remaining whole blood will be centrifuged at 1500 g for 10 minutes at 4°C. The separated plasma will be pipetted evenly into two separate eppendorfs and frozen at -80°C for subsequent analysis of metabolic content using FIE-MS and GC-MS. Two 1.5 µL aliquots of whole blood will be transferred from the 1.mL aliquot into separate test cartridges and will be analysed for HbA1c and lipid profile by an automated point of care blood analyser (Afinion 2, Abbot, Cheshire, UK).

Urine Treatment:

Urine samples will be centrifuged at 1500 g for 10 minutes at 4°C. 1ml of supernatant will be pipetted evenly into two separate eppendorfs and frozen at -80°C prior to analysis of metabolic content using FIE-MS and GC-MS.

20. End of Trial

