The testing stage of this study will be defined as finished when the last participant completes the final visit (6 month testing). Additionally, the research will be stopped if there is a lack of

recruitment after 6 months or if a clinical or research incident prompts a review.

21. Statistics and Data Analysis

A computerized statistical package will be used to analyse all data associated with the primary and secondary outcomes (SPSS version 17.0, SPSS inc., Chicago, IL). Normally distributed data will be presented as mean \pm SD. Scores from the questionnaires will be calculated based upon their respective scoring protocols. A two factor mixed model ANOVA will be conducted on all physiological measures and questionnaire responses to determine any differences between groups over time. Significant differences identified by the ANOVA will be further analysed by post hoc independent or paired t-tests with Bonferroni correction. Data mining of urine samples using methods such as PCA will be employed to determine if foods can be discriminated. Statistical significance will be accepted at $P < 0.05$.

22. Sample Size Calculation

The sample size was decided based upon potential numbers of eligible patients provided to the research team by the participating general practice. Potential numbers are based upon the amount of registered patients with a $\text{BMI} > 25 \text{ kg/m}^2$ or an existing $\text{HbA1c} < 12$ months. As this is a feasibility study for a future large scale randomised control trial, no formal sample size calculation has been employed.

23. Planned Recruitment Rate

Previous work completed by the research team demonstrated an approximate 50% uptake in consultation offers in patients with pre-diabetes ($n = 420$). Our partnering surgery currently have 737 patients with a $\text{BMI} > 25 \text{ kg/m}^2$. A further 216 patients have an HbA1c (recorded within the last year) within the eligible range. Furthermore, Church surgery identifies approximately 6 new

‘at risk’ individuals each week. Therefore, we estimate it will take one month to recruit 40 patients into the study.

24. Data Management

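### Section 21 has no rule for incomplete visits, and the two-factor mixed ANOVA, read in its usual sense, discards follow-up data that a mixed model in the same package would keep

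*Combined protocol and SAP*

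**What the plan says.** Section 21 gives the analysis in one sentence, "A two factor mixed model ANOVA will be conducted on all physiological measures and questionnaire responses to determine any differences between groups over time", and the follow-up in another: "Significant differences identified by the ANOVA will be further analysed by post hoc independent or paired t-tests with Bonferroni correction". The software is "SPSS version 17.0, SPSS inc., Chicago, IL". No SPSS procedure is named, and nothing is said about random effects, covariance structure or likelihood estimation.

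Section 18 says "Participants are free to withdraw from the study at any time without giving prior warning or reason for withdrawal" and "Participants will not be replaced if withdrawn". Section 13 has participants attend "on 3 separate occasions, for baseline, 3 month and 6 month testing". Section 4 sets the question that the analysis must answer: "Secondary research questions aim to determine the impact of the consultation on the following measures at 3 and 6 months".

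No section defines an analysis population, a missing-data method, an expected dropout rate or a sensitivity analysis for these outcomes. Section 4 does make completion of each visit a primary feasibility measure, so incomplete follow-up is anticipated.

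**The concern.** Two factors, an ANOVA and post hoc independent or paired t-tests together describe the classical between-within design. That analysis needs a value at every level of the time factor, so a patient with a gap is dropped from it. For an outcome taken at all three visits:

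- a patient who attends at 3 months and then leaves loses the 3-month value as well;
- a patient who misses only 3 months loses the 6-month value as well.

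The post hoc t-tests are separate analyses and might use whatever pairs are available. They run only on effects that the ANOVA has flagged, however, so the completers still decide what is examined.

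Two things are at stake. One is the loss of data from a small study. The other is a possible bias in the arm contrast, if leaving depends on early response and does so differently in the two arms. In that case the 3-month values that would largely correct the bias have been collected but are left out.

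**Working it through.** The plan derives no sample size, power or dropout figure, so there is nothing to reproduce. Everything below is illustration under stated assumptions.

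**Inputs.**
- Number randomised: 40, from the recruitment estimate in section 23. This is an assumption, because section 22 gives no formal sample size.
- Miss rate *m* per follow-up visit: not given. The only attrition figure is in section 2, for the earlier uncontrolled study: 79 + 44 + 0 + 7 = 130, with 7 lacking follow-up data, so 7/130 = 5.4%. That was at 12 months in a different design. It is used here as the low end of a range, with 10%, 15% and 20% as further assumed values.

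**Loss with independent misses at 3 and 6 months.** Complete = 40(1 − m)²; seen at 6 months = 40(1 − m); dropped although one of the two follow-up visits was attended = 40 × 2m(1 − m).

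| m | Kept by the ANOVA | Seen at 6 months | Dropped with one follow-up visit |
|---|---|---|---|
| 5.4% | 35.8 | 37.8 | 4.1 |
| 10% | 32.4 | 36.0 | 7.2 |
| 15% | 28.9 | 34.0 | 10.2 |
| 20% | 25.6 | 32.0 | 12.8 |

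**Loss with withdrawal only and no return.** Everyone seen at 6 months was also seen at 3 months, so the ANOVA loses nobody who was seen at 6 months. It loses only the 3-month data of those who leave between the two visits. If a proportion m leaves in each interval, that is 40 × m(1 − m) = 2.0, 3.6, 5.1 or 6.4 patients at the four rates.

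**Bias, dropout driven by change.** Assume no true effect, SD of HbA1c change 2 mmol/mol and correlation 0.7 between 3- and 6-month change. In one arm only, 35% of those who have worsened by 3 months leave, against 5% of the rest, which is 20% overall. The mean of the positive half of a normal distribution with SD 2 is 1.596.
- Completers' mean change at 3 months: 0.5 × 1.596 × (0.65 − 0.95) / 0.80 = −0.299, or 0.15 SD of change.
- At 6 months: 0.7 × (−0.299) = −0.209, or 0.10 SD of change.
- A simulation of 1,000,000 patients gave −0.299 and −0.207. An estimate using all 3-month data gave +0.003 at 6 months.
- Standard error of the arm difference with 20 per arm: 2 × √(2/20) = 0.63. The biases are 0.47 and 0.33 of one standard error.

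**Bias, other dropout rules.** These use correlation 0.7 between all pairs of visits and no true effect. Units are SDs of the outcome; the SD of change is √(2 × 0.3) = 0.77 of that.
- Random dropout, or the same dependence on the 3-month value in both arms: arm contrast within 0.003 of zero.
- Dependence on the 3-month level in one arm only: −0.050 at 3 months and 0.007 (not material) at 6 months.
- Dependence on the change from baseline in one arm only: −0.12 at 3 months and −0.06 at 6 months.

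The results differ because of the dropout rule. Dropout on level with equal correlations shifts completers' baseline and 6-month values by the same amount, which cancels in the change. Dropout on change does not cancel.

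**The case against.** The strongest reply is that casewise deletion is inferred from a method name. Some people use the term mixed model ANOVA for a linear mixed model, which keeps incomplete patients. That is possible, but the rest of section 21 points to the classical reading, and under either reading the text needs the same clarification.

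Several stronger readings are tempting and the documents do not support them.
- A reader might infer that one missed visit removes a patient from every comparison of that outcome. Section 21 does not say which cases enter the t-tests.
- A reader might infer that all measures need three visits. Section 13 schedules the food frequency questionnaire at baseline and 6 months only, and the diabetes questionnaire components at baseline only.
- A reader might attribute the gap of 29 kept against 34 seen to the withdrawal rule. That gap needs intermittent misses, and withdrawal alone does not produce it.
- A reader might assume that controls have little reason to stay. Usual care is not withheld (section 3), the invitation letter gives prevention advice to all (section 9), and controls attend the same research visits (section 13). Dropout that differs by arm is a possibility; the documents do not show it.

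It is also fair that the losses are modest at the only attrition rate on record (about two patients between those kept and those seen at 6 months), that the biases are below half a standard error, and that these are secondary outcomes of a feasibility study. Reporting completion as a primary measure will make attrition visible, but it does not correct the comparison.

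**Conclusion.** The point holds in a conditional form. Section 21 does not say how incomplete visits are treated, and on the most natural reading of its wording the ANOVA discards follow-up data already collected. With 40 randomised and independent misses of 5.4% to 20% per visit, it keeps about 36 to 26 patients against 38 to 32 seen at 6 months. With withdrawal only, the loss is limited to the 3-month data of later leavers.

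Bias in the arm contrast is possible and is not established. It is about zero if dropout is random or follows the same pattern in both arms. In the arm-specific scenarios tried it was about 0.05 to 0.15 SD at 3 months and from nothing material to 0.10 SD at 6 months. It would be wrong to conclude that the planned analysis is necessarily biased or that the feasibility aims are compromised. The change is worth making because a better method is available in the same software at small cost.

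**What to change.** For outcomes measured at three visits in all participants (HbA1c, cholesterol, BMI, waist and hip girth, blood pressure, body composition, IPAQ-SF and SF-36), replace the ANOVA in section 21 with a likelihood-based linear mixed model, using SPSS MIXED. Specify group, visit and group-by-visit, an unstructured within-patient covariance and Satterthwaite degrees of freedom. Include all available visits of every randomised patient, in the randomised arm, whether or not a visit was missed, the patient later withdrew or the consultation was attended. Estimate the arm differences at 3 and 6 months from that model, and keep the completers' ANOVA as a sensitivity analysis.

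Report the ActiGraph subgroup descriptively or with a simpler covariance: with 5 patients per arm, the six parameters of an unstructured matrix would rest on at most 10 patients.

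The cost is some rewording of section 21 and a different procedure in the same package. The model assumes that missingness depends only on observed data. That cannot be verified, but it is weaker than what the completers-only analysis needs.

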Pre-diabetes is defined as a higher than normal blood glucose concentration and is associated with an increased risk of developing diabetes; of those identified as pre-diabetic 5 – 10% will develop diabetes within 12 months while a similar percentage will revert to normal blood glucose levels (Tabak et al., 2012). Furthermore, those with pre-diabetes are at an increased risk of developing a range of complications (e.g. Ford et al., 2010). It has been reported that the prevalence of pre-diabetes in England increased dramatically between 2003 and 2011, with the prevalence in those over the age of 16 years, increasing from 11.6% to 35.3% (Mainous et al., 2014). If unchecked the increase in the diabetic and pre-diabetic populations will pose an unsustainable burden on the health care service. It is widely accepted that diet and physical activity play an important role in reducing the risk of developing diabetes. The Diabetes Prevention Program Research Group has shown that diabetes may be preventable by lifestyle intervention targeting diet and exercise (Knowler et al., 2002). Despite this, three in every four adults in the UK are not consuming the recommended five portions of fruit and vegetables per day and one in every three are not reaching the minimum recommendations for physical activity (Statistics on Obesity, Physical Activity and Diet, 2017), figures which go some way to explain the increase in prevalence of pre-diabetes. In 2015 a North Ceredigion GP Cluster initiated a pre-diabetes intervention which targeted patient education and lifestyle modification (Thatcher & Gregory, 2017. Welsh Endocrine and Diabetes Society, Spring Meeting, Cardiff). The intervention comprised of a 30-minute one-to-one consultation with a practice nurse for those identified as having a glycated haemoglobin (HbA1c) of between 42 and 47 mmol·mol⁻¹. The 30-minute consultation included the collection of baseline data on diet and exercise and stressed the importance of avoiding developing diabetes and what steps could be taken to avoid this. The design did not include a control group, as such, direct comparisons with usual care cannot be made, however, twelve months post the consultation there were statistically significant

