Upon completion of this phase of data collection, participants will be provided with a series of validated questionnaires to complete (to be completed at every visit unless otherwise stated). These include; the International Physical Activity Questionnaire- Short Form (IPAQ-SF), Food Frequency Questionnaire (FFQ; EPIC-Norfolk; baseline and 6 months), SF-36 (36-Item Short Form Survey Instrument) and components of the Personal Diabetes Questionnaire (baseline). Participants will complete the questionnaires unassisted although members of the research team will be available to answer any questions the participant may have relating to the questionnaires. Lastly, participants will receive instructions on the use of the urine collection kit for dietary monitoring (see below) and the ActiGraph for physical activity monitoring (if randomised; see below). Participants will then be free to leave the laboratory. An additional acceptability questionnaire designed by the research team will be given to participants at the end of the 6 month visit and will include questions relating to the WARU visits, 15 minute consultation (if received), urine collection and ActiGraph use. Visits will last between approximately 120 minutes and 150 minutes depending on the time taken for participants to complete the relevant questionnaires.

Following completion of the baseline visit, participants will be randomised into either the intervention group (INT) or the control group (CON). Randomisation will be achieved using a minimisation software package (Minim) and will ensure that there will be only minor differences between groups in the variables used in the allocation process. Participants in INT will receive a focussed 15 minute one to one consultation with a practice nurse at their registered general practice. The consultation derives from the original 30 minute protocol employed during a previous study conducted by the present research team (Thatcher and Gregory, 2017) which used 104 GP-registered patients. The first half of the 30 minute consultation in that study (led by general practise) collected baseline data (height, weight, waist circumference, blood pressure)

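### Section 21 does not say that only a group-by-time effect opens the paired post hoc tests, so regression to the mean in range-selected HbA1c could appear as a within-arm fall

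*Combined protocol and SAP*

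**What the plan says.** Section 21 plans the main analysis as follows: "A two factor mixed model ANOVA will be conducted on all physiological measures and questionnaire responses to determine any differences between groups over time". The next sentence reads: "Significant differences identified by the ANOVA will be further analysed by post hoc independent or paired t-tests with Bonferroni correction". The threshold is given as "Statistical significance will be accepted at" P < 0.05, with no statement of sidedness. The section does not name the ANOVA term that leads to post hoc testing. It does not say how a within-arm change is to be interpreted, and it plans no adjustment for baseline. Regression to the mean is not mentioned anywhere in the document.

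HbA1c is checked twice before randomisation. Section 7 admits patients who "have an HbA1c (recorded within the last year) of between 42 and 47" mmol/mol. Section 13 then applies the range again at the research unit: "Should patients HbA1c be outside the required values during the baseline visit, they will be informed and will take no further part in the research". Randomisation follows the baseline visit (section 13), so both arms pass the same two checks. The 3- and 6-month readings are subject to no range.

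Section 4 lists the impact of the consultation on HbA1c as a secondary question. The primary aims are counts and percentages for eligibility, consent and completion.

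**The concern.** The baseline HbA1c is both an entry criterion and the pre-value of any baseline-to-follow-up paired test. When people are kept because a noisy reading fell in a band, later readings move on average towards the mean of the population they came from. The movement is common to both arms, so it shows up in the ANOVA as a time effect. If a time effect is enough to open paired tests, the drift can produce a significant fall in the consultation arm when the consultation does nothing.

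The protocol already recognises how little a before-after change can show. Of the earlier cluster project, section 2 says: "The design did not include a control group, as such, direct comparisons with usual care cannot be made". The study is meant to inform a larger trial and to be published (sections 2, 22 and 27). A within-arm fall read as an effect could therefore carry over into that trial's planning.

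**Working it through.** **1. Which term opens the tests.** A two-factor mixed ANOVA with group (2) and visit (3) yields a group, a time and a group-by-time term. The stated purpose of the ANOVA points to group-by-time. The post hoc sentence refers only to significant differences from the ANOVA and allows paired tests, which in this design compare visits within participants. Both readings fit the text, so both are calculated.

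**2. Inputs.** The plan has no figure of its own to reproduce: section 22 reports no formal sample size calculation.

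- From the document: 40 patients (section 23), half without the intervention (section 3), so 20 per arm; three visits; surgery and baseline readings both 42 to 47; alpha 0.05; Bonferroni.
- Assumed: two-sided tests; Bonferroni over three visit pairs (0.05/3 = 0.0167); mean true HbA1c of the source pool (mu), between-person SD (s) and within-person plus assay SD (e), all in mmol/mol. The document gives none of the last three.

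**3. Size of the drift.** With two readings in the band and true values distributed N(mu, s²), let m be the mean baseline reading among those kept. The expected change from baseline to an unrestricted later reading is

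change = −[e² / (2s² + e²)] × (m − mu).

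For mu = 40, s = 3, e = 1.5, the factor is 2.25 / (18 + 2.25) = 0.111. Allowing for rounding to whole units, m must lie between 41.5 and 47.5. The fall is then between 0.111 × 1.5 = 0.17 and 0.111 × 7.5 = 0.83. Simulation gives 0.42 to 0.43. The direction turns at the middle of the band, (42 + 47)/2 = 44.5: a lower pool mean gives a fall, a higher one a rise.

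**4. False-positive rates with no consultation effect.** The simulation applied both range checks, the 2 × 3 mixed ANOVA, then within-arm paired tests against baseline at P < 0.0167 (4,000 trials per row). A fall means a significant decrease in INT at 3 or 6 months.

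| mu / s / e | Drift | Time effect significant | Fall in INT, any term opens | Same, but not in CON | Fall in INT, interaction only |
|---|---|---|---|---|---|
| 40 / 3 / 1.5 | −0.43 | 24.6% | 8.7% | 7.5% | 1.5% |
| 38 / 3 / 2 | −1.04 | 74.1% | 36.3% | 22.2% | 2.8% |
| 42 / 4 / 1 | −0.07 | 5.3% | 1.9% | 1.8% | 0.9% |
| 44.5 / 3 / 1.5 | 0.00 | 4.9% | 1.0% | 1.0% | 0.5% |
| 46 / 3 / 2 | +0.24 | 8.0% | 0.3% | 0.3% | 0.2% |

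The Monte Carlo standard error of the 8.7% is √(0.087 × 0.913 / 4000) = 0.4 percentage points. Further runs of 6,000 and 8,000 trials gave 8.5% to 8.6% for the first row (7.0% in INT but not CON) and 34% to 35% for the second. At a pool mean of 43 the rate is about 1.3% to 1.5%.

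**5. The randomised comparison.** For pool means 38 to 42, the group-by-time test is significant in 4.2% to 5.6% of trials, and a between-arm t-test on the 6-month change in 4.4% to 5.6%. Both are close to the nominal 5%, because both arms drift equally.

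**6. What the earlier cohort shows.** Of 130 patients in the band, 79 stayed, 44 fell below 42, none rose above 47 and 7 had no data (79 + 44 + 0 + 7 = 130). Of those followed, 44/123 = 36% fell below the band. This fits downward drift, but the cohort received the consultation and had no control group, so it cannot separate drift from effect.

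**The case against.** The strongest reply is that the sentence introducing the ANOVA says it looks for group differences over time, so the differences followed up are naturally the interaction. Paired tests would then only describe an interaction already found, and the rate of a spurious fall would be about 0.5% to 3%. That reading is reasonable and may be the intended one. It is not written down, and one clause would settle it.

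Second, a reader might infer that unrestricted paired tests are planned. In the central scenario these would show a fall in INT at either follow-up visit in 24% of trials, and in INT but not CON in 18%. Section 21 does not support those figures: it requires a significant ANOVA result first and Bonferroni correction second, and the rates that apply are about 8.5% and 7%.

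Third, a reader might infer that the trial repeats the earlier project's uncontrolled design. It does not. There is a control arm, randomised after both range checks and included in the same ANOVA. Nor does any passage say that a within-arm change will be taken as proof of effect. What stands is narrower: the plan permits a within-arm test and gives no rule for reading it.

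Fourth, the direction and size of the drift rest on values the document does not give. This stands in full. A pool mean below 44.5 is plausible because one search route is simply BMI above 25 kg/m² (sections 9 and 10), but it remains an assumption.

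**Conclusion.** The point holds as an ambiguity in section 21 with a measurable consequence for HbA1c. If any significant ANOVA term opens the paired tests, a no-effect trial shows a significant fall in the consultation arm in about 8.5% of cases under the central assumptions, against about 1% without drift. The range is about 1.3% to 35% for pool means 38 to 43, between-person SD 3 to 4 and within-person SD 1 to 2. Near the top of the pool-mean range the problem is negligible, and above 44.5 the drift reverses.

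It would be wrong to conclude that the trial's comparison of the two arms is biased: regression to the mean affects both equally and the between-arm tests keep their 5% level. The primary feasibility outcomes are untouched. Severity is low to moderate.

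**What to change.** Add two statements to section 21:

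- Post hoc tests follow only a significant group-by-time term, and the impact of the consultation is judged from the INT minus CON difference in change at 3 and 6 months, reported with a confidence interval.
- Within-arm changes are reported descriptively (mean and confidence interval) and not as evidence of effect, noting that regression to the mean in HbA1c is possible because entry required a baseline reading of 42 to 47 mmol/mol.

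No visit, sample or measurement changes. The cost is that within-arm P values no longer support claims of effect; the within-arm estimates themselves are kept.

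### Section 21 uses significance tests at P < 0.05 to judge effectiveness on many secondary measures in a feasibility study not sized for them, with no lead outcome and no planned between-arm estimate or confidence interval

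*Combined protocol and SAP*

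**What the plan says.** Section 4 makes feasibility the primary aim, measured by a count of patients in the HbA1c range and by consent and completion percentages. Its secondary part reads "Secondary research questions aim to determine the impact of the consultation on the following measures at 3 and 6 months", followed by eight lines: HbA1c, cholesterol, BMI, waist and hip girth, blood pressure, body composition, physical activity and diet. None is ranked first.

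The section 5 sentence opens by calling this a feasibility study, but gives the purpose of the design as "to assess the effectiveness of a 15 minute one to one consultation compared to no treatment".

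Section 21 states: "A two factor mixed model ANOVA will be conducted on all physiological measures and questionnaire responses to determine any differences between groups over time". It continues: "Significant differences identified by the ANOVA will be further analysed by post hoc independent or paired t-tests with Bonferroni correction". The threshold is given as "Statistical significance will be accepted at" P < 0.05. The section plans mean ± SD for normally distributed data. It does not plan a between-arm difference with a confidence interval, does not adjust across outcomes, and does not call the tests exploratory.

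Section 22 bases the size on the practice's numbers of potentially eligible patients and says that, this being a feasibility study, "no formal sample size calculation has been employed". The only recruitment number is 40, in the section 23 estimate.

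**The concern.** Omitting a power calculation is normal in a feasibility study. The difficulty is combining that omission with an analysis whose only stated criterion for an effect is P < 0.05, applied separately to many measures.

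- **False positives.** The Bonferroni step works within one measure after its ANOVA is significant. It does nothing about the number of measures tested.
- **The wrong contrast.** A two-factor mixed ANOVA gives a group effect, a time effect and a group-by-time interaction, and the plan does not say which supports a claim. A time effect alone could lead to paired t-tests, and so to a significant change within one arm. That is not the randomised comparison. Both arms are selected on an HbA1c window (section 8), and both receive a letter with steps to avoid diabetes (section 9), so change without the consultation is plausible.
- **Weak nulls.** At the likely size, a non-significant HbA1c result says little about moderate effects.

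The study is meant to inform a main trial. A stray significant result or an uninformative null could mislead that planning, where an estimate with its interval would show how little is known.

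**Working it through.** **The plan's own figure.** The plan states no power, effect size or SD, so 40 cannot be reproduced from a sample-size formula. The figures below take 40 from section 23, split about equally (section 3 says half the cohort will not receive the intervention), giving 20 per arm. This is an assumption: section 22 states no number, and section 18 keeps recruitment open for 6 months.

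**1. Chance of at least one false positive.** Inputs: 0.05 per test (section 21), one test per measure, no true effects. For k independent tests the chance is 1 − 0.95^k.

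- k = 8 (the section 4 list): 1 − 0.95^8 = 0.337
- k = 13: 1 − 0.95^13 = 0.487
- k = 14: 1 − 0.95^14 = 0.512

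Simulating equally correlated normal test statistics gives, for correlations of 0.3 / 0.5 / 0.7:

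- k = 8: 30% / 25% / 19%
- k = 13: 42% / 33% / 24%

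One way to reach 13 is HbA1c, total and HDL cholesterol, BMI, waist, hip, systolic and diastolic pressure, fat mass, percentage fat, and one score each from IPAQ, FFQ and SF-36. ActiGraph would make 14. The documents do not fix this count. Eight may be low, since SF-36 is a questionnaire covered by section 21 but is not on the section 4 list. Reading more than one ANOVA effect per measure would also raise the chance.

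**2. Detectable difference and precision, unadjusted, at one visit.** Two-sided 5% level, outcome SD = 1, noncentral t.

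- 20 per arm: 80% power needs 0.91 SD. Power is 34% at 0.5 SD and 15% at 0.3 SD.
- 95% CI half-width at 20 per arm: t(0.975, 38 df) × √(2/20) = 2.024 × 0.316 = 0.64 SD.
- 15 per arm (assumed 25% loss; section 18 does not replace withdrawals): 80% power needs 1.06 SD, half-width 0.75 SD.
- For scale, 80% power at 0.5 SD needs 63 per arm (normal approximation).

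**3. With baseline adjustment.** At an assumed baseline-to-follow-up correlation of 0.7, the SD shrinks by √(1 − 0.7²) = 0.714.

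- Difference for 80% power at 20 per arm: 0.91 × 0.714 = 0.65 SD.
- CI half-width: 0.64 × 0.714 = 0.46 SD.
- Power at 0.5 SD: 58%.

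**4. ActiGraph subgroup.** Section 13 gives monitors to 5 per arm. If these data were tested, 80% power would need 2.02 SD and the half-width would be 1.46 SD.

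**The case against.** The strongest defence is that this is a feasibility study, its primary outcomes are descriptive, and the tests concern secondary questions only. That stands, and it limits how serious the point is. It also rules out several stronger readings that a reader might infer.

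- *The size has no basis.* Section 22 gives a pragmatic basis and a reason for having no formal calculation. What is missing is a power or precision basis for the tests.
- *A false positive is more likely than not.* For the 8 listed measures the figure is 34% at most with one test each. About half is reached only with 13-14 independent variables. BMI, girths and body composition are unlikely to be independent.
- *Everything is tested.* The feasibility outcomes have no stated hypothesis test, and urine data go to methods such as PCA. The Personal Diabetes Questionnaire (baseline only) and the acceptability questionnaire (6 months only) cannot show change over time. Section 21 does not name ActiGraph.
- *A null result is worthless.* An interval of about ±0.64 SD could still argue against very large effects.
- *Only significant measures will be reported, or the main-trial decision turns on a P-value.* No section says so.

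It is also fair that the 0.91 SD and 0.64 SD figures are not the precision of the planned analysis, because a mixed ANOVA over repeated visits uses within-person correlation. Even with adjustment at 0.7, though, power at 0.5 SD stays below 80%. Nothing in the defence supplies a lead outcome, a named contrast or an interval.

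**Conclusion.** The point holds for the secondary analyses. Section 21 assesses effect by significance at P < 0.05 without control across outcomes, without saying which ANOVA effect matters, and with a route to within-arm claims. No between-arm estimate or interval is planned.

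The false-positive risk is substantial: about one in three for the 8 listed measures if independent, and about 19-30% at correlations of 0.7 to 0.3. The detectable difference at 20 per arm is 0.91 SD unadjusted, or about 0.65 SD with baseline adjustment at an assumed correlation of 0.7. These figures rest on 40 participants, equal arms, no loss and a two-sided 5% level, and a larger final sample would improve them. A non-significant HbA1c result would be weak evidence rather than evidence of no effect. The feasibility outcomes are not affected.

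**What to change.** - **Section 5, and the matching wording in the abstract and the secondary objectives of section 4:** replace assessing effectiveness or determining impact with estimating the effect of the consultation to inform a main trial. The primary aim can stay, because there effectiveness refers to the future trial.
- **Section 21:** replace the P < 0.05 and post hoc t-test sequence as the basis for effect claims. Report baseline-adjusted between-arm differences at 3 and 6 months (6 months only for the FFQ, which is not given at 3 months) with 95% CIs. Label them exploratory and put HbA1c at 6 months first. That ordering is a judgement, but it follows the stated interest in blood glucose control. Keep the planned SDs for sizing the main trial.
- **ActiGraph (5 per arm):** report any data descriptively.
- **Conclusions:** base them on the feasibility outcomes.

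The cost is rewording; visits, samples and participants do not change. The downside is that the sponsor can no longer claim significant secondary effects.
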